Population:	
Aim 1: Patients ≥ 65 years admitted to one of the study inpatient units
 
Aim 2a: Any patient ≥ 18 years admitted to one of the study inpatient units with ADRD/delirium
 
Aim 2b: Adult Caregiver of any patient in aim 2a

Intervention:	Palliative Care Educator using video decision aid shown at time of admission to patients/caregivers in wards/units randomized to the intervention phase
Objectives:	The overall objective of the present proposal is to reduce the burden of COVID-19 and advanced illness and its consequences for an aging U.S. population.
Design/Methodology:	This project is a multi-center stepped wedge cluster randomized trial of an advance care planning (ACP) video intervention (vs. standard of care) using a Palliative Care Educator among patients ≥ 65 years OR any patient ≥ 18 years old with ADRD regardless of age admitted to one of the study inpatient units
Total Study Duration:	2 years
Subject Participation Duration:	EHR data collection during the 16 months of enrollment (2 months baseline plus 14 months intervention steps). EHR data abstracted for one year after the end of the 16 months of enrollment.

3 Background/Rationale & Purpose

3.1 Background Information

COVID-19 disproportionately affects the elderly and those with Alzheimer's Disease and Related Dementias (ADRD/Delirium).^{1, 2} The COVID-19 pandemic has killed over 500,000 Americans and is a common and morbid condition, especially in people over the age of 65 and those with functional impairment and ADRD/Delirium.² When COVID-19 strikes, these patients die at higher rates.^{2, 3} The surge in patients with COVID-19 poses a significant public health challenge and has the potential to compromise the orderly function of health institutions.⁴

The palliative care needs of inpatients with ADRD/Delirium and those over 65 is rapidly increasing, and access to palliative care clinicians is limited. The majority of hospitals in the U.S. have palliative care programs; indeed, over the past decade access to palliative care services has increased dramatically.⁵⁻⁹ However, staffing capacity to meet the clinical needs continues to be a significant challenge.¹⁰⁻¹³ Many hospitals provide palliative care services only to a small portion of the patients that would be appropriately served by palliative care^{14, 15} and the scope of this problem has increased with COVID-19. New models are needed for palliative care services to meet the need.¹⁶ Older patients and those with ADRD/Delirium face the prospect of receiving burdensome and unwanted end-of-life care due to lack of palliative care services.

Decision making in patients with ADRD/Delirium and their caregivers during COVID-19 is urgent. Patients with ADRD/Delirium have a small window of opportunity to state their preferences for the advanced stages of the disease before their disease makes them incapable of decision making. Without an Advance Care Planning (ACP) discussion, caregivers are often left to make treatment decisions for their loved ones with the advanced stages of the disease.¹⁷ Numerous studies have shown that caregiver decision making is no better than chance and often lacks stability over time.¹⁸ Caregivers often suffer a great deal of burden and distress attempting to develop a comprehensive care plan for the advanced stages of the disease.¹⁷ Caregiver stress and communication challenges are exacerbated by their exclusion from the hospital.¹⁹⁻²¹ COVID-19 poses significant ACP challenges for patients with ADRD/Delirium and their caregivers.

This study will be conducted in compliance with the protocol, applicable regulatory requirements, and BMC/BU Medical Campus Human Research Protection policies and procedures.

3.2 Rationale and Purpose

Advance care planning (ACP) in older patients or patients with ADRD/Delirium needs improvement: ACP seeks to ensure that patients receive medical care consistent with their values, goals and preferences during serious and chronic illness.²² The lack of ACP documentation is associated with greater use of aggressive interventions, more terminal hospitalizations, lower hospice use, higher health care costs, and worse family bereavement

outcomes.^{17, 22} Unfortunately, ACP documentation in older patients and patients with ADRD/Delirium remains inadequate.^{23, 24} Furthermore, marked racial and regional disparities persist in ACP documentation for seriously ill patients.²⁵ For the ACP process to lead to optimal decisions, patients and their caregivers require accurate, impartial and comprehensible information about their treatment options, and a care setting where communication needs are addressed early in their illness by a dedicated clinician.²⁶⁻²⁸ However, studies show that traditional written and verbal ACP does not effectively inform many patients and caregivers, and often occurs late in the disease process.²² High-quality ACP increases patient safety by ensuring that patients receive effective care that meets their goals.

Video decision support improves ACP: The traditional approach to ACP, which primarily relies on ad hoc verbal descriptions of hypothetical clinical situations and treatment choices, is limited because complex scenarios are difficult to envision, provider information is inconsistent, and verbal explanations are hampered by literacy, emotional and language barriers.^{22, 29-31} Over the past few years, investigators have recognized the shortcomings of prior efforts and have developed new interventions to better facilitate ACP.^{22, 32-37} The video intervention proposed for this study focuses on patient, caregiver and clinician communication about treatments for medical care facilitated by a Palliative Care Educator (PCE).

The COVID-19 PCE video intervention proposed for this study focuses on patient/caregiver and clinician communication about goals of care. Video aids to better educate and inform decision making are commonly used. These videos attempt to overcome language and literacy barriers and to present potential scenarios with a sense of reality lacking in verbal descriptions.⁵⁴⁻⁵⁶ These videos are available in 25 different languages, and attempt to overcome literacy barriers and to present potential scenarios with a sense of reality lacking in verbal descriptions. In addition to using videos, our PCEs will be trained in the Vital Talk program, the most widely disseminated teaching method that focuses on patient-centered serious illness communication skills training. To our knowledge, this is the first trial of PCEs trained in communication skills to engage patients with palliative care services with videos. If effective, this model can be rapidly disseminated to improve care for millions of Americans.

Hospitalized patients often receive burdensome interventions as the default option, without a shared decision-making conversation or awareness of more comfort-oriented care.^{57, 58} Thus, patients are at high risk of receiving poor-quality care at the end of life given the burden of such care on patients. Poor ACP and communication about patients' preferences for end-of-life care contribute substantially to the receipt of aggressive, costly, and unwanted medical care for patients with serious illness.^{31, 46, 48, 59-62} Therefore, improving palliative care services may prove to be an effective strategy to enhance the delivery and quality of medical care for hospitalized patients. ACP video tools have shown promising efficacy in educating patients about their options and informing their preferences for care.^{55, 63-66} Given the intensity of health care utilization for hospitalized patients, patients may greatly benefit from a PCE-led video intervention to expand the reach and impact of palliative care to inform and empower patients and their caregivers in the decision-making process and to improve the delivery of care that is concordant with their wishes during COVID-19.

4 Objectives

4.1 Study Objectives

The **overall objective** of this study is to reduce the burden of COVID-19 by expanding the reach of inpatient palliative care services, especially for patients with ADRD/Delirium. We propose to conduct a stepped wedge cluster randomized trial (SW-CRT) of a PCE video intervention among hospitalized patients aged 65 and over, or any patient ≥ 18 years with ADRD/Delirium and their caregivers in the ward and ICU settings of two major hospitals: Boston Medical Center (BMC) and North Shore University Hospital. Patient outcomes will be abstracted from electronic health records with Natural Language Processing (NLP).

We will test our hypotheses via the following **Specific Aims**:

Aim 1: To test the effects of a PCE video intervention leveraging video decision aids on the quality of end-of-life care. We will conduct a SW-CRT to evaluate intervention effectiveness by comparing the following outcomes among 9,000 hospitalized patients: ACP documentation; preferences for resuscitation; palliative care consults; and, hospice use. **Hypotheses:** *A higher proportion of patients in the intervention phase (vs. control) will: (1) complete advance care plans (primary outcome), (2) have documented resuscitation preferences, (3) have palliative care consults, (4) enroll in hospice over the course of one year of follow-up, and (5) have documented health care proxies.*

Aim 2a: The manual chart review activity is intended only for the patients whose caregiver participated in the survey activity. It is distinctive from the NLP activities described in our protocol which identify ACP documentation from the free-text of clinical notes. The chart review will involve a thorough human review of structured ACP elements such as DNR/DNI order, MOLST/POLST and Health Care Proxy form completion in each patient's chart.

Aim 2b: To characterize caregiver-centered outcomes of patients with ADRD/Delirium, including: (1) knowledge, (2) confidence in future care, (3) communication satisfaction, (4) decisional satisfaction, and (5) decisional conflict in 600 caregivers of patients with ADRD/Delirium admitted to the hospital. **Hypothesis:** *Intervention phase caregivers of patients with ADRD/Delirium (vs. control) will have higher knowledge, confidence, communication satisfaction, decisional satisfaction, and lower decisional conflict.*

IMPACT: COVID-19 poses a unique dilemma for older Americans and patients with ADRD/Delirium and their caregivers, who must balance their desire to live against the risk of a lonely and potentially traumatic hospital death. Video decision support is a practical, evidence-based, and innovative approach to assist patients facing such choices. We have a highly experienced team and infrastructure at BMC and North Shore to execute this proposal. If proven

effective, this innovative care model can be immediately deployed across the country to improve the quality of care for millions of Americans. Given the urgency of the need for scalable interventions, this study will provide the evidence quickly and efficiently to improve care rapidly across the country.

4.2 Study Outcome Measures

4.2.1 Primary Outcome Measures

The primary outcome of this trial is ACP documentation any time during the index hospitalization as ascertained by NLP-assisted EHR review for any qualifying documentation of ACP in the EHR note (goals of care, advance directive, MOLST/POLST, code status, palliative care or hospice) (yes versus no).

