PCEs will receive Vital Talk intensive communication skills training via a highly structured series of Zoom conferences. The PCEs will also be trained on use of the ACP certified videos using the ACP App. Training will instruct clinicians on how to: 1. Introduce the videos to patients and caregivers; 2. Use the videos as adjuncts to ACP counseling by clinicians; 3. Select the appropriate video(s) from the entire suite according to patients' needs; and, 4. Prescribe videos for patients and caregivers using the electronic platform. The suite of ACP videos is designed to address common ACP decisions confronting patients at risk or with COVID-19 and their caregivers. The videos also cover all of the decision points surrounding ADRD/Delirium (e.g., feeding tubes, resuscitation, etc.). The videos are intended to be an adjunct to clinician counseling, not to replace it. Suggested videos for clinicians to use with patients will include goals-of-care videos, general ACP videos, intervention-specific videos such as ventilatory support or CPR, and hospice videos. PCEs will also have an array of videos to support caregivers, including videos regarding compassionate extubation if this is relevant.

The PCE will encourage the patient to make their wishes known to their family or other caregiver (and will offer to facilitate a call/video-call) and the attending, and that with the patient's

permission, will relay their wishes to the treating team in addition to completing ACP documentation in the EHR. As an integrated part of existing hospital practice, PCE will communicate with the primary treating team and the palliative care team. When there are palliative care needs beyond ACP (e.g., symptom control) or if the PCE determines that the support of the full palliative care team is warranted, the PCE will recommend to the treating team to place the consult request. The PCE will not be collecting any data for research purposes only. For QI purposes, the Palliative care consult team will keep tracking documents of the PCE activities (number of patients seen per day, amount of time spent with each patient, etc). This is needed for supervisory purposes. These may be reviewed retrospectively by the research team and compared to research data. In this case, an amendment will be submitted to the IRB to cover these activities.

9 Study Procedures

Eligibility

Aim 1 and Aim 2a: Each day, PCEs will review a list of inpatients who are ≥ 65 or have a diagnosis of ADRD/Delirium

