Every 2 months (the size of each step; 1 baseline + 7 steps = 8 data transfers) the outcomes of interest using NLP will be transferred to our data collection site (DFCI). Data on the following outcomes will be collected until the end of the study period.

- ACP discussion (e.g., goals-of-care discussion, advance directive, MOLST/POLST, code status, etc.)
- Resuscitation preferences
- Palliative care consults
- Hospice Use
- Health care proxy discussion

As stated above, direct identifiers will be held at each respective site (BMC researchers can see BMC identifiers but not North Shore University Hospital's identifiers, and vice versa.) The risks will be minimal as the data will be stored and analyzed on a HIPAA secure cluster at each site. None of the data will be stored in paper form. The data and identifiers will be kept for seven years after the end of the study period on the HIPAA secure cluster computer at each site. After the seven years, all HIPAA identifiers and all linking codes will be permanently destroyed in accordance with regulation.

NLP Validation

Prior to the use of NLP for outcome assessment in this trial, we will entrain and validate the NLP process for each of our two study sites. Specifically, we will use historic note data from a sample of 20 patients from each site who meet enrollment criteria. We will then measure the validity of this process by comparing results from human assisted NLP to a human chart review. The goal of the keyword library validation process is to ensure that the keyword library and abstraction guidelines accurately represent the language used to communicate information associated study outcomes. The semi-automated note annotation process will be cross-validated across both sites. Clinical notes will be the substrate of this process and must be requested from each site's clinical data warehouse.

Each site will ensure that the appropriate IRB and Data Sharing protocols are in place before this activity begins.

Chart Review

EHR data will be extracted by manual chart review on all Aim 2a patients whose caregiver completes a survey (2b). This survey will be limited to the inpatient stay that generated the survey, and include the following elements for collection of secondary outcomes:

- DNR/DNI order
- MOLST/POLST filed
- Resuscitation/Intubation preferences
- Health Care Proxy specified
- Palliative Care Consult during hospitalization

- Discharge Disposition

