A detailed chart review instrument is attached to the protocol.

Withdrawal

We do not anticipate any circumstances where the caregiver will withdraw from participation in the study. Study staff will make clear to the caregiver that participation is entirely voluntary and may be withdrawn at any time.

Masking

Due to the nature of the intervention, participants and staff will not be blinded to the intervention.

The NLP outcomes adjudication process is not fully automated in this study. We are doing a human-assisted NLP process in which a staff member validates the text presented in the software as a possible outcome. For NLP analysis, the following steps will be taken to ensure blinding to study step assignment by the staff member doing the NLP outcome attribution:

- Prior to adjudication activities, names will be coded
- Annotation will be performed in large batches with all patients enrolled who have clinical notes to that point.
- NLP notes for adjudication will not be grouped by Study ID when presented to annotators. Each note will be annotated individually, without reference to concepts contained in other notes annotated before or after.
- When possible, a staff member who did not enroll the participants will perform the annotation.

Caregiver Surveys

Caregivers will be surveyed using a REDcap survey. The REDCap project will be hosted by BUMC, both sites will enter data into the same project. All subjects will be assigned a unique identifier that will be entered into REDCap. All other PHI will be retained in a linking file that is not shared outside the institution.

Caregiver data will be linked with the associated patient EHR data, but this linking file will be kept locally, and only HIPAA LDS will be shared with other sites included on this protocol.

Costs/Payment

There are no costs to subjects for participating in this study.

Caregivers will be compensated \$50 for completing the survey.

10 Assessment of Safety and Data Safety Monitoring Plan (DSMP)

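### The primary outcome reads note text only, so ACP held solely as an order or filed form scores no; this miss may differ by phase, and no planned analysis checks it

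*Combined protocol and SAP*

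**What the plan says.** Section 4.2.1 defines the primary outcome as ACP documentation during the index hospitalization, "as ascertained by NLP-assisted EHR review for any qualifying documentation of ACP in the EHR note". The qualifying content is "goals of care, advance directive, MOLST/POLST, code status, palliative care or hospice) (yes versus no".

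Section 4.1 (Aim 2a) separates two activities. The NLP methods are those "which identify ACP documentation from the free-text of clinical notes". The manual review is different: "The chart review will involve a thorough human review of structured ACP elements such as DNR/DNI order, MOLST/POLST and Health Care Proxy form completion". Its scope is limited: "The manual chart review activity is intended only for the patients whose caregiver participated in the survey activity". Section 9 (Chart Review) assigns that review to secondary outcomes.

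Section 9 (Masking) confirms the unit that is read: "Each note will be annotated individually, without reference to concepts contained in other notes annotated before or after".

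Section 8 says that the educator, with the patient's permission, passes the patient's wishes to the treating team "in addition to completing ACP documentation in the EHR". It does not say whether that documentation is a note, a form or an order.

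The sensitivity analyses in 12.3 deal with repeat hospitalizations, patients who contribute to both phases, and missing data. None deals with where in the record the ACP was found.

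**The concern.** By the plan's own division, DNR/DNI orders, MOLST/POLST and proxy forms are structured elements that the NLP does not read. For about 96% of Aim 1 patients nothing else reads them for the primary outcome. A patient with a DNR order and a filed MOLST, neither mentioned in any note, scores no. A patient with one goals-of-care sentence scores yes.

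If this miss were equal in the two phases, it would only lower both rates. But the intervention acts on how ACP is recorded as well as on whether it happens, so the miss may be unequal. The Aim 1 hypothesis in 4.1 and 12.1 concerns patients completing plans. A change in where plans are recorded could be read as a change in how many exist, or could conceal such a change. A larger sample does not remove this, and blinded annotation does not help, because a record that never enters a note never reaches the annotator.

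**Working it through.** **1. The plan's own figures (12.2).** Inputs: 25% vs 35%, two-sided alpha 0.05, stated power 80%, 440 per group, design effect 2.72. The pooled-variance formula without continuity correction gives 329 per group at 80% power and 440 at 90%, so 440 matches 90% power. That errs on the safe side and does not affect this point. The next step reproduces: 440 x 2 x 2.72 = 2393.6, i.e. 2394.

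**2. Reach of the structured review.** 600/15,000 = 4.0% (12.1, 12.2). With the 9,000 given in 4.1 it is 600/9,000 = 6.7%.

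**3. Shift toward a false gain.** Let s be the share of all control patients whose ACP exists only as an order or form with no mention in any note. Let r be the fraction of such patients who also have a note under the intervention. If the intervention creates no new ACP:

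- apparent difference, note-only outcome = s x r
- apparent difference, note-or-structured outcome = 0

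The documents give neither s nor r, so the values below are assumptions. The chance of a significant result uses a control note rate of 25% (12.2), equal groups, n per group = N/(2 x 2.72), and standard error = sqrt(2 x p x (1 - p)/n) with p the mean of the two rates.

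| s | r | Apparent gain | Chance significant, N = 2,394 | N = 15,000 |
|---|---|---|---|---|
| 2% | 25% | 0.5 points | 4% | 6% |
| 5% | 50% | 2.5 points | 13% | 56% |
| 10% | 50% | 5 points | 38% | 99% |

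For the last row at N = 15,000: n = 15,000/5.44 = 2,757; p = 0.275; standard error = sqrt(2 x 0.275 x 0.725/2,757) = 1.20 points; z = 5/1.20 = 4.2.

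**4. What the assumed s implies.** As a share of all control-phase ACP, s = 2% means 2/27 = 7% is never mentioned in a note; s = 10% means 10/35 = 29%.

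**5. Shift toward no effect.** Suppose the intervention truly adds 10 points but half of the added records are forms or orders only. The note-only outcome shows 10 x (1 - 0.5) = 5 points, and power at N = 2,394 falls from 90% to 38%.

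**6. Could the plan detect either case?** NLP validation (section 9) uses historic notes from 20 patients per site. It compares human-assisted NLP with human chart review before the trial, so it cannot show whether capture differs between phases. The chart review of surveyed patients, planned as about 300 per phase, could show this, but 12.3 specifies no such comparison.

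**The case against.** A reader might infer that any ACP recorded as an order or form scores no. The documents do not support that. MOLST/POLST, code status and advance directive are all qualifying note content, so an order or form mentioned in any note of the index stay scores yes. Only ACP that no note mentions is missed, and that group may be small.

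A reader might also infer that the trial is biased toward finding an effect. That is not shown either. Section 8 does not say what the educator writes, and if the educator mainly files forms the bias runs the other way.

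The size rests wholly on assumption. At 2% x 25% it is negligible, and s = 10% requires more than a quarter of control-phase ACP to go unmentioned in every note. Section 12.2 also puts effect size ahead of p-values and sets 10 points as the benchmark for clinical significance; a spurious 5 points falls short of that.

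Two textual points also count. Section 12.3 words the primary hypothesis as completing ACP documentation, which is closer to 4.2.1 than the wording in 4.1 and 12.1. It also describes the resuscitation outcome as orders, which might suggest a structured source, although section 9 lists that outcome under NLP collection. The statement in section 9 that "Clinical notes will be the substrate of this process" concerns keyword-library validation and is not evidence about trial outcome ascertainment; 4.1 and 4.2.1 carry that point without it.

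All of this stands. It limits the claim but does not close the gap: no passage adds orders or forms to the primary outcome, and no planned analysis measures what is missed.

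**Conclusion.** The concern holds in a limited form. ACP recorded only outside notes is invisible to the primary outcome, structured review covers about 4% of patients, and the intervention includes documentation, so the miss may differ by phase. The direction is unknown. Under assumed s and r the false gain runs from about 0.5 points (2% x 25%) to 5 points (10% x 50%), i.e. from negligible to half the benchmark. An understatement is equally possible if the educator's work ends in forms. This is reason to measure the gap and to limit the wording of the conclusion. It does not establish that the note-based primary outcome is invalid or must be replaced.

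**What to change.** 1. Keep the note-based primary outcome in 4.2.1.
2. In 12.3, prespecify a sensitivity analysis for all Aim 1 patients that scores yes for a qualifying note or a structured entry made during the index stay: a non-default code-status order and, where these can be queried, a filed MOLST/POLST or advance directive. Leave out default full-code orders. Use the two-monthly EHR extractions already described in 11.5.
3. From the chart review already planned for surveyed patients, report by phase the share with structured ACP but no qualifying note. This estimates s directly.
4. State in section 8 whether the educator records ACP as a note, a form or both.
5. Word the conclusion as an effect on note documentation unless both versions agree.

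Cost: a modest extra data pull. Its size is uncertain for filed forms, because the plan obtains these by manual review and does not say that they can be queried. The combined control rate may exceed 25%, so the planning rates should not be read across to it. The chart-review subset covers only ADRD/delirium patients, some of them from the added control-only units (7.1), and its intervention patients are surveyed after the educator's contact. It therefore informs the size of the gap but cannot correct the Aim 1 estimate. With about 300 charts per phase and s = 10%, the 95% margin is 1.96 x sqrt(0.1 x 0.9/300) = 3.4 points per phase before clustering.
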